## 6. RESPONSE DEFINITIONS

6.1. Patients' overall response will be assessed after at least 2 cycles of treatment but no more than after 6 cycles, and each cycle is 28 days.

### 6.2. Study Endpoints

**6.2.1. Primary Efficacy Endpoint:** The overall response rate (CR + PR + HI) based on the IWG-2006 criteria detailed below. Responses must last at least 4 weeks per definition.

#### Complete Remission:

- Bone marrow:  $\leq 5\%$  myeloblasts with normal maturation of all cell lines
- Persistent dysplasia will be noted
- Peripheral blood
  - o Hemoglobin  $\geq 11\text{g/dL}$
  - o Platelets  $\geq 100 \times 10^9/\text{L}$

- Neutrophils  $\geq 1.0 \times 10^9/L$
- Blasts 0%

**Partial Remission:**

- All CR criteria if abnormal before treatment except:
  - Bone marrow blasts decreased by  $\geq 50\%$  over pretreatment but still  $> 5\%$

**Stable Disease:**

- Failure to achieve at least PR, but no evidence of progression for  $>8$  weeks

**Failure:**

- Death during treatment or disease progression characterized by worsening of cytopenias or significant increase in percentage of bone marrow blasts

**Hematologic Improvement (HI) Response Criteria\*:** responses must last at least 8 weeks

- **Erythroid response** (if pretreatment hemoglobin  $< 11g/dL$ )
  - Hemoglobin increase by  $\geq 1.5g/dL$
  - Relevant reduction of units of RBC transfusions by an absolute number of at least 4 RBC transfusions/8 wk compared with the pretreatment transfusion number in the previous 8 wks. Only RBC transfusions given for a Hgb of  $\leq 9.0 g/dL$  pretreatment will count in the RBC transfusion response evaluation
- **Platelet response** (if pretreatment platelets  $< 100 \times 10^9/L$ )
  - Absolute increase of  $\geq 30 \times 10^9/L$  for patients starting with  $> 20 \times 10^9/L$  platelets
  - Increase from  $< 20 \times 10^9/L$  to  $> 20 \times 10^9/L$  and by at least 100%
- **Neutrophil response** (if pretreatment  $< 1.0 \times 10^9/L$ )
  - At least 100% increase and an absolute increase of  $> 0.5 \times 10^9/L$

\*Pretreatment counts averages of at least 2 measurements (not influenced by transfusions) for at least one week

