#### **6.2.3. Secondary Efficacy Endpoints**

The key secondary endpoints for this study are:

- To evaluate the safety and tolerability of the combination of eltrombopag and decitabine. Safety will be assessed by the overall incidence and severity of all study-treatment related adverse events per CTCAE v 4.0
- To evaluate the incidence of dose reductions and delays of decitabine therapy
- To evaluate the effect of eltrombopag on medically significant hemorrhagic events (defined as Grade 3 or 4 hemorrhagic events on CTCAE v 4.0)
- To evaluate the effect of eltrombopag on platelet and RBC transfusion independence per IWG-2006 criteria
  - o Platelet IWG-2006: A complete response is defined as a platelet count  $> 100 \times 10^9/L$ ; and a major response defined as an increase of platelet count by higher than  $30 \times 10^9/L$ .
  - o Durable platelet count: in which a hematologic improvement in platelets (HI-P) defined as either an increase  $\geq 30 \times 10^9/L$  from patients with a baseline platelet count  $\geq 20 \times 10^9/L$ , or an increase from  $< 20 \times 10^9/L$  to  $\geq 20 \times 10^9/L$  and by at least 100%, present for  $\geq 8$  weeks.
- Incidence of transformation to AML per FAB criteria ( $>30\%$  blasts) during treatment period and follow-up
- Incidence and severity of bone marrow fibrosis during treatment period and follow-up
- To examine the relationship between clinical response with ferritin level and other markers of iron burden at study start

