## 8.3. Analysis of Key Study Endpoints

The primary endpoint is overall response rate (ORR). The ORR will be evaluated along with the exact 95% confidence interval. Secondary endpoints include platelet response, durable platelet response, transformation to AML, incidence of bone marrow fibrosis, and time-to-event outcomes such as progression-free survival (PFS) and overall survival (OS). The probabilities of PFS and OS will be estimated using the method of Kaplan and Meier. The incidence rates of other binary secondary endpoints will be estimated, along with the exact 95% confidence intervals. Subjects that discontinue the study prior to having achieved a clinical response will be considered to have not had an event.

**Patients receiving growth factors other than eltrombopag (erythropoietin, GM-CSF or G-CSF) will not be considered in the HI analysis for the time periods specified in Section 4.5.3 Supportive Care Guidelines. Hemoglobin levels and platelet counts collected from patients that have received a transfusion within the last 7 days will not be considered in the analysis.**

Survival or times to failure and time to progression functions will be estimated using the Kaplan-Meier method. The two-sided log-rank test will be used to assess the differences of time to events between groups.

The total number of dose administrations, the average dose (mg), and the cumulative dose administered will be summarized by eltrombopag treatment group.

Blood chemistry and complete blood counts will be summarized by treatment group at each time point.

Additional exploratory analyses of the key study endpoints will be performed as deemed appropriate.

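### The platelet improvement rules for the primary ORR and for durable platelet response differ at 20 × 10⁹/L, and the primary rule leaves a pretreatment value of exactly 20 unassigned

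*Combined protocol and SAP*

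**What the plan says.** All counts here are in units of 10⁹/L. Section 6.2.1 defines the primary endpoint as "The overall response rate (CR + PR + HI) based on the IWG-2006 criteria detailed below", so the HI criteria in that section decide who counts in the ORR.

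The platelet part of those criteria has two rules:
- Upper group: "Absolute increase of $\geq 30 \times 10^9/L$ for patients starting with $> 20 \times 10^9/L$ platelets".
- Lower group: "Increase from $< 20 \times 10^9/L$ to $> 20 \times 10^9/L$ and by at least 100" percent.

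The HI criteria add that "responses must last at least 8 weeks". Their footnote sets the starting value: "Pretreatment counts averages of at least 2 measurements (not influenced by transfusions) for at least one week".

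Section 6.2.3 defines platelet HI again for the durable platelet endpoint, also for at least 8 weeks. There, a rise of at least 30 applies to a baseline of 20 or more, "or an increase from $< 20 \times 10^9/L$ to $\geq 20 \times 10^9/L$ and by at least 100" percent.

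Section 8.3 makes the second definition an analysed endpoint: "Secondary endpoints include platelet response, durable platelet response". I take its durable platelet response to be the durable item in Section 6.2.3. Section 3.1 (criterion 4) admits patients with a count of 100 or less and sets no lower limit, so 20 is an eligible starting value. No section reconciles the two definitions.

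**The concern.** Two definitions carry the same name, cite the same criteria and require the same duration, yet they classify some patients differently. The primary rule uses strict inequalities on both sides of 20, so an eligible patient whose averaged pretreatment value is exactly 20 cannot be a platelet responder, however large the rise. The secondary rule has no such gap.

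Whoever programs the analysis must code both rules. The same patient could then be a durable platelet responder in one table and a platelet non-responder in the primary analysis. Noticing this after responses are known would mean choosing a rule with the data in view. The trial is open-label and single-arm, and Section 8 has efficacy data reviewed quarterly.

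**Working it through.** The plan states no figure on this point, so the check is to apply both rules as written.

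Let *b* be the pretreatment value and *f* the count sustained for at least 8 weeks.

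- Section 6.2.1: *b* < 100, and either (*b* > 20 and *f* − *b* ≥ 30) or (*b* < 20, *f* > 20 and *f* ≥ 2*b*).
- Section 6.2.3: either (*b* ≥ 20 and *f* − *b* ≥ 30) or (*b* < 20, *f* ≥ 20 and *f* ≥ 2*b*).

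| Pretreatment value | Section 6.2.1 requires | Section 6.2.3 requires | Result |
|---|---|---|---|
| 10 or less | *f* > 20 and *f* ≥ 2*b* | *f* ≥ 20 and *f* ≥ 2*b* | differ at *f* = 20 only |
| above 10, below 20 | *f* ≥ 2*b*, already above 20 | the same | agree |
| exactly 20 | no rule | *f* ≥ 20 + 30 = 50 | differ for every *f* ≥ 50 |
| above 20, below 100 | *f* ≥ *b* + 30 | the same | agree |

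Comparing the rules for every whole-number *b* from 1 to 100 and *f* from 0 to 400 confirms the table. Examples:

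- 20 to 49: neither rule is met.
- 20 to 50, or 20 to 60: not met in Section 6.2.1, met in Section 6.2.3.
- 10 to 20: not met in Section 6.2.1, met in Section 6.2.3.
- 10 to 21, or 19 to 38: both met.

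The comparison also shows one difference away from 20. A baseline of exactly 100 is eligible and lies outside the below-100 condition in Section 6.2.1, but Section 6.2.3 does not exclude it.

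**Effect on the ORR.** With the 40 patients of Section 4.1, one reclassified patient moves the ORR by 1/40 = 2.5 percentage points.

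**Effect on the design.** None. Section 8 treats response as a yes/no count. With the beta(1.2, 0.8) prior, the rule Pr(ORR < 0.6) > 0.95 reproduces the Table 1 limits: 3 of 10 (0.962), 8 of 20 (0.957) and 13 of 30 (0.963). One more response gives 0.878, 0.901 and 0.922, and the trial continues. The Table 2 stopping probabilities also reproduce (0.971, 0.775, 0.391, 0.105, 0.015). None of these depends on how platelet response is defined.

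**The case against.** The strongest reply is that this is a wording slip with almost no practical reach. Most of that stands.

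- The rules agree for every starting value above 10 and below 20, and for every value above 20 and below 100.
- Section 6.2.1 averages at least two untransfused counts, so exactly 20 should be uncommon. For a patient starting at 10 or less, the sustained count must be exactly 20, which is close to a rounding event.
- There is no doubt which text governs the ORR: Section 6.2.1 points to its own criteria.
- The two endpoints need not be identical. Sections 4.1 and 8 limit the primary analysis to four cycles, while Sections 6.2.3 and 8.3 give the durable response no such window. A difference in time window would remain after the signs are aligned.
- The documents do not reproduce the IWG-2006 publication, so they cannot show which wording matches it.

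These points limit the size of the problem. They do not explain why one named response has two sets of cut-offs, or why one set omits an eligible value.

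A reader might infer more, in three ways that the documents do not support:

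- **That anyone starting at 20 is an ORR non-responder and a durable responder.** Without a gain of at least 30 for 8 weeks, the patient meets neither rule. With it, the patient may still enter the ORR through CR, PR, erythroid HI or neutrophil HI.
- **That the frequency can be read from Section 2.1** (67% of referred patients below 100, over 10% below 20). That series describes MDS patients at referral, not the advanced MDS enrolled here. It says nothing about averaged values of exactly 20. At best it would bear on how often a patient starts at 20, not on how often the ORR changes.
- **That the mismatch threatens the futility looks.** It would need a reclassified patient with no other qualifying response and a count sitting on the limit at that look. The documents give no frequency for such patients.

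**Conclusion.** The inconsistency is real and follows from the text alone. Two kinds of patient meet the Section 6.2.3 definition but are not platelet responders under Section 6.2.1: those starting at exactly 20 who gain at least 30 for at least 8 weeks, and those starting at 10 or less whose sustained count is exactly 20. They are lost from the ORR only if they have no CR, PR, erythroid HI or neutrophil HI.

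The effect is small. Each such loss costs 2.5 points of ORR at 40 patients, cases should be rare, and no sample size, stopping limit or operating characteristic changes. The conclusion assumes that both definitions are applied as written and that the durable platelet response in Section 8.3 is the item defined in Section 6.2.3. The expected number of affected patients cannot be estimated from the documents.

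**What to change.** Before response data are reviewed, reconcile Sections 6.2.1 and 6.2.3:

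1. Adopt one set of platelet cut-offs, checked against the cited IWG-2006 criteria, that assigns every pretreatment value, including exactly 20, to one group and uses one sign for the level to be reached from below 20.
2. In Section 6.2.3, replace the second definition with a reference to the platelet rule in Section 6.2.1, including its averaged pretreatment value. If the durable response is meant to have a different assessment period, state that there.

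The cost is a few inequality signs and a cross-reference. No new data are needed, and Tables 1 to 4 stay as they are.

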**Progression or relapse after HI†:**

- At least 1 of the following:
  - At least 50% decrement from maximum response levels in granulocytes or platelets
  - Reduction in hemoglobin by  $\geq 1.5\text{g/dL}$
  - Transfusion dependence
- ‡In the absence of another explanation, such as acute infection, repeated courses of chemotherapy (modification), gastrointestinal bleeding, hemolysis, and so forth. It is recommended that the 2 kinds of erythroid and platelet responses be reported overall as well as by the individual response pattern.

**Relapse after CR or PR:**

- At least 1 of the following
  - Return to pretreatment bone marrow blast percentage
  - Decrement of  $\geq 50\%$  from maximum remission/response levels in granulocytes or platelets
  - Reduction in hemoglobin concentration by  $\geq 1.5\text{g/dL}$  or transfusion dependence

**Cytogenetic Response:**

- Complete: Disappearance of the known chromosomal abnormality without appearance of new abnormalities in 20 metaphases
- Partial: At least 50% reduction of the chromosomal abnormality in 20 metaphases

**Disease Progression:**

For patients with:

- Less than 5% blasts:  $\geq 50\%$  increase in blasts to  $> 5\%$  blasts
- 5-10% blasts:  $\geq 50\%$  increase to  $> 10\%$  blasts
- 10-20% blasts:  $\geq 50\%$  increase to  $> 20\%$  blasts
- 20-30% blasts:  $\geq 50\%$  increase to  $> 30\%$  blasts

Any of the following:

- At least 50% decrement from maximum remission/response in granulocytes or platelets
- Reduction in hemoglobin by  $\geq 2$  g/dL
- Transfusion dependence

#### **Survival Endpoints:**

- Overall: death from any cause
- Event free: failure or death from any cause
- PFS: disease progression or death from MDS
- DFS: time to relapse
- Cause specific death: death related to MDS

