### **1.2 Secondary Objectives**

The secondary objectives of the study are:

- To evaluate the safety and tolerability of the combination of eltrombopag and decitabine. Safety will be assessed by the overall incidence and severity of all study-treatment related adverse events per CTCAE v 4.0
- To evaluate the incidence of dose reductions and delays of decitabine therapy
- To evaluate the effect of eltrombopag on medically significant hemorrhagic events (defined as Grade 3 or 4 hemorrhagic events on CTCAE v 4.0)
- To evaluate the effect of eltrombopag on platelet and RBC transfusion independence per IWG-2006 criteria
- Incidence of transformation to AML per FAB criteria (>30% blasts) during treatment period and follow-up
- Incidence and severity of bone marrow fibrosis during treatment period and follow-up
- To examine the relationship between clinical response with ferritin level and other markers of iron burden at study start

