### **3. STUDY ELIGIBILITY**

#### **3.1 Inclusion Criteria**

1. Signed, informed consent must be obtained prior to any study specific procedures.
2. Subjects with a histologically confirmed diagnosis of MDS by FAB criteria, including both MDS and RAEB-T (AML with 20-30% blasts and multilineage dysplasia) and chronic myelomonocytic leukemia (CMML) with at least 10% bone marrow blasts by World Health Organization (WHO) classification are eligible.
3. Advanced MDS by virtue of intermediate-2 or high-risk MDS by IPSS score, or high or very-high risk by IPSS-R.
4. Platelet count  $\leq 100 \times 10^9/L$  at baseline
5. Eastern Cooperative Oncology Group (ECOG) performance status of 0 to 2
6. Adequate liver function, as evidenced by a serum bilirubin  $\leq 2x$  the ULN (except for patients with a confirmed diagnosis of Gilbert's Disease) and an ALT or AST  $\leq 3x$  the laboratory ULN.
7. Serum creatinine  $\leq 2.5x$  upper limit of normal
8. Subjects must be  $\geq 18$  years of age at the time of informed consent
9. Subject is practicing an acceptable method of contraception (documented in chart). Female subjects (or female partners of male subject) must either be of non-childbearing potential (hysterectomy, bilateral oophorectomy, bilateral tubal ligation or post-menopausal  $> 1$  year), or of childbearing potential and use one of the following highly effective methods of contraception (i.e. Pearl index  $< 1.0\%$ ) from 2 weeks prior to administration of study medication, throughout the study, and 28 days after completion or premature discontinuation from the study:

- Complete abstinence from intercourse;
- Intrauterine device (IUD);
- Two forms of barrier contraception (diaphragm plus spermicide, and for males condom plus spermicide);
- Male partner is sterile prior to entry into the study and is the only partner of the female;
- Systemic contraceptives (combined or progesterone only).

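### For patients entering with more than 20% and up to 30% blasts, transformation to AML need not count as a PFS event

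*Combined protocol and SAP*

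**What the plan says.** Four parts of the protocol bear on this point.

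- **Eligibility (Section 3.1, criterion 2)** admits FAB-defined disease, "including both MDS and RAEB-T (AML with 20-30% blasts and multilineage dysplasia". Patients can therefore enter just below the AML cut-off.
- **AML endpoint (Sections 1.2 and 6.2.3)** is "Incidence of transformation to AML per FAB criteria (>30% blasts) during treatment period and follow-up". It sets an absolute threshold with no condition on relative change. Section 8.1 plans a Kaplan-Meier analysis of time to transformation.
- **Progression (Section 6.2.1, Disease Progression)** sets a blast rule by band. For the top band it is "20-30% blasts: $\geq 50\%$ increase to $> 30\%$ blasts"; for the band below, "10-20% blasts: $\geq 50\%$ increase to $> 20\%$ blasts". A second list follows, headed as any one of several items: "At least 50% decrement from maximum remission/response in granulocytes or platelets", a hemoglobin fall of at least 2 g/dL, or transfusion dependence. AML transformation is in neither list.
- **PFS (Section 6.2.1, Survival Endpoints)** is "PFS: disease progression or death from MDS". Section 8.3 lists it among the secondary endpoints, with Kaplan-Meier estimation.

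No section says whether transformation to AML counts towards PFS.

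**The concern.** In the top band the blast rule has two conditions, a relative rise and an absolute level, while the AML endpoint has only the absolute level. A patient can satisfy the second without the first. Unless another progression item is met, that patient is an AML event in one Kaplan-Meier analysis and still at risk, event-free, in the other.

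This would occur in the patients who enter closest to AML. Their PFS could look longer than a reader would expect, since most readers would assume that a patient who has transformed is no longer progression-free. If the question is left open until the data are in, whether to count such patients becomes a choice made with the results in view.

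**Working it through.** The plan states no sample size, power or event count for PFS or AML transformation, so there is no planned figure to reproduce. The check compares the two rules directly.

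**Inputs.** Let b be blasts at entry and x blasts at a later marrow, both in percent.
- AML (Sections 1.2 and 6.2.3): x > 30.
- Blast progression, top band (Section 6.2.1): x ≥ 1.5 × b and x > 30. This reads the increase as relative and measured from the entry value.
- Discordant window, AML met but blast rule unmet: 30 < x < 1.5 × b. Its width is 1.5 × b − 30 points.

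| Entry blasts b | 1.5 × b | Discordant window | Width (points) |
|---|---|---|---|
| 20% | 30% | none | 0 |
| 21% | 31.5% | above 30% to below 31.5% | 1.5 |
| 22% | 33% | above 30% to below 33% | 3 |
| 25% | 37.5% | above 30% to below 37.5% | 7.5 |
| 28% | 42% | above 30% to below 42% | 12 |
| 30% | 45% | above 30% to below 45% | 15 |

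**Entry at 20% or below.** Since 1.5 × 20 = 30, any value above 30% is a rise of at least 50% and also exceeds the cut-off of the patient's band. Crossing 30% is then always progression, although the PFS definition does not name it. A 20% entry value falls in two bands, but neither leaves a gap.

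**Worked case.** Entry 25%, later marrow 35%. AML: 35 > 30, met. Blast progression: 35 < 37.5, not met. If counts, hemoglobin and transfusion status hold, there is no PFS event.

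**Sensitivity to what the text leaves open.**
- *Reference value.* Section 6.2.1 does not say whether the rise is from entry or from the lowest value reached. From the lowest value, the window shrinks for a patient whose blasts first fell, and it closes if they fell to 20% or less (1.5 × 20 = 30). It is unchanged for a patient whose blasts never fell.
- *Type of increase.* If 50% meant percentage points, the window at a 30% entry value would run to just under 80% (30 + 50), and lower bands would be affected too. The relative reading is the natural one.
- *Second list.* If its items are alternatives to the blast rule, some patients in the window will progress that way. If they were required as well, discordance would be wider. The text does not say which.

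**The case against.** The strongest reply is that the blast rule is only part of the progression definition. Read as alternatives, the count, hemoglobin and transfusion items may catch a patient whose marrow is worsening. That stands: discordance is possible, not certain. It does not remove the gap, because none of those items is AML transformation. The granulocyte and platelet item needs a fall from a best response, which a patient with steady counts does not show.

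A second reply is that little depends on PFS. It is absent from the objectives in Section 1.2 and from the key secondary list in Section 6.2.3, and it is descriptive in a single arm. This also stands and limits the weight of the point. Section 8.3 nevertheless commits to reporting it.

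A third is that counting a move from 29% to 31% as an event is a matter of preference. That is fair, and the fix should make such cases visible.

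A reader might infer more than the documents support:
- *That AML transformation is never a PFS event.* It always is, through the blast rule, for entry at 20% or below.
- *That progression generally stays unmet up to 45% blasts.* That limit applies only at a 30% entry value, with the rise measured from entry.
- *That the number of misclassified patients can be given.* If 10-25% of the 40 patients entered in this band (an assumption the documents do not support), 0.10 × 40 = 4 to 0.25 × 40 = 10 would be exposed. Those who land in the window and meet no other item are an unknown part of that number.
- *That the two endpoints cannot be reconciled.* AML has its own incidence and time-to-event analysis, so a listing of discordant patients would reconcile them.

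**Conclusion.** The point holds for patients entering with more than 20% and up to 30% blasts. In that stratum, transformation to AML without a rise of at least 50%, and without any other progression item, is not a PFS event, so PFS can be overstated there. The window is 1.5 × entry blasts − 30 points, from zero at 20% to 15 points at 30%.

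This rests on a relative increase measured from the entry value, with the second list of items as alternatives to the blast rule. On that reading, entry at 20% or below is unaffected. The effect on the PFS estimate cannot be quantified, because the documents do not give the number of patients expected in the stratum or how many would land in the window. The primary endpoint and both stopping rules do not change. This is an inexpensive clarification that should be made before analysis; it is not a flaw in the main design.

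**What to change.** Change the PFS definition under Survival Endpoints in Section 6.2.1, and only that definition. The event becomes disease progression, transformation to AML (more than 30% blasts, dated at the first marrow showing it), or death as already listed. This closes the window at every entry value. In the analysis plan, add:

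- AML incidence reported separately for entry blasts up to 20% and above 20% to 30%;
- a listing of any patient whose only PFS event is crossing 30% without a rise of at least 50%;
- PFS shown also under the existing progression rule alone.

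Leave the Disease Progression criteria unchanged. Section 4.2.2 ties discontinuation of treatment to progression, so editing those criteria could alter a treatment rule. The sponsor should reconcile the progression criteria, the PFS definition and Section 4.2.2, so that the endpoint change does not affect discontinuation.

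The cost is one line in the definition, one extra table split, one listing and one additional curve. No new data are needed: Section 5.2 already schedules marrows every cycle for four cycles, then every three cycles as clinically indicated, and at end of treatment. No sample size or power figure changes. The downside is that PFS may be slightly shorter and a small rise across 30% counts as an event; the listing and the second PFS analysis make that visible.

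### PFS counts only deaths from MDS and is estimated by Kaplan-Meier, so the curve ignores other deaths before progression and overstates the chance of being alive and progression-free

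*Combined protocol and SAP*

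**What the plan says.** The list of survival endpoints in section 6.2.1 of the protocol gives PFS as "PFS: disease progression or death from MDS". The same list gives overall survival as "Overall: death from any cause" and event-free survival as "Event free: failure or death from any cause", and it has a separate entry, "Cause specific death: death related to MDS". The limit on cause in the PFS line therefore reads as intended, not as shorthand for all deaths.

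Section 8.3 names PFS among the secondary endpoints and states: "The probabilities of PFS and OS will be estimated using the method of Kaplan and Meier". It adds: "Survival or times to failure and time to progression functions will be estimated using the Kaplan-Meier method". Failure is defined earlier in 6.2.1 as "Death during treatment or disease progression characterized by worsening of cytopenias or significant increase in percentage of bone marrow blasts", with no limit on the cause of death.

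No section says how a non-MDS death without progression enters the PFS analysis, gives a competing-risk method, or says who decides for this endpoint whether a death was due to MDS.

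**The concern.** A reader takes a PFS curve as the proportion of patients alive and free of progression. Under this definition it is not. A patient who dies of another cause before progressing is neither an event nor still at risk, so Kaplan-Meier can only drop that patient as censored. The method then treats the patient as if progression could still have been observed later.

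This is not a remote case here. Section 2.3 describes hepatotoxicity and thromboembolism as risks of eltrombopag, and a death of either kind need not be attributed to MDS. Section 2.1 cites hemorrhagic deaths of 14 to 24% in an MDS population, and the plan does not say whether a fatal bleed or infection in a cytopenic patient counts as an MDS death. The answer moves the estimate, and section 8 describes the trial as open label.

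At stake is one reported secondary estimate, which would look better than the quantity its name implies and would carry no trace of toxic deaths.

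**Working it through.** **Inputs.** The event definition comes from 6.2.1 and the estimator from 8.3. The documents give no PFS median, event count, power or follow-up target, so there is no stated figure to reproduce. The hazards and shares below are assumptions for illustration.

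**Direction.** A patient with a non-MDS death leaves the risk set at that time under either definition, so the two Kaplan-Meier estimates share the same risk sets. The all-cause estimate has an extra factor below 1 at each such death. The protocol's curve can therefore never lie below the all-cause curve, and it lies above it once such a death has occurred before progression. This needs no model.

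**Size.** Let λ1 be the hazard of progression or MDS death, and λ2 the hazard of non-MDS death before progression, both constant and independent.

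- Protocol PFS by Kaplan-Meier estimates exp(−λ1·t).
- All-cause PFS is exp(−(λ1+λ2)·t).
- With share = λ2/(λ1+λ2), protocol median ÷ all-cause median = (λ1+λ2)/λ1 = 1/(1 − share).

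*View A: all-cause median fixed at 10 months.* All-cause PFS at 12 months is 2^(−1.2) = 43.5%. Protocol PFS at 12 months is 2^(−1.2·(1 − share)).

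| Share | Protocol median (months) | Protocol 12-month PFS |
|---|---|---|
| 10% | 10/0.9 = 11.1 | 2^(−1.08) = 47% |
| 20% | 10/0.8 = 12.5 | 2^(−0.96) = 51% |
| 30% | 10/0.7 = 14.3 | 2^(−0.84) = 56% |

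*View B: protocol median fixed at 10 months, non-MDS deaths added.* The protocol curve stays at 43.5% at 12 months whatever λ2 is.

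| Share | All-cause median (months) | All-cause 12-month PFS |
|---|---|---|
| 10% | 10 × 0.9 = 9.0 | 39.7% |
| 20% | 10 × 0.8 = 8.0 | 35.4% |
| 30% | 10 × 0.7 = 7.0 | 30.5% |

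**Count with 40 patients.** Suppose k patients die early of other causes and half of the remaining 40 − k progress by 12 months. Kaplan-Meier with those deaths censored gives 50% for every k. The proportion alive and progression-free is 0.5·(40 − k)/40, which is 47.5%, 45%, 42.5% and 40% for k = 2, 4, 6 and 8.

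**Against a competing-risk display.** In view B with a 20% share, 1 minus the cumulative incidence of progression or MDS death at 12 months is 1 − 0.8·(1 − 0.354) = 48.3%. The protocol's 43.5% lies between this and the all-cause 35.4%. It is the observed probability of neither outcome.

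**The case against.** **The curve does not rise with toxic deaths.** A reader might infer that PFS looks better the more patients die of toxicity. The plan does not support that. Under independent hazards exp(−λ1·t) does not contain λ2, and view B and the 40-patient count show the curve standing still while all-cause PFS falls. The larger medians in view A come from holding the all-cause rate fixed, so a larger share means fewer disease events. They measure the gap between two definitions, not an effect of added toxic deaths. A real rise would need the censored patients to differ in their risk of progression, and nothing in the documents shows that. This objection stands in full.

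**Toxic deaths are not lost from the whole analysis.** Section 8.3 plans overall survival, which counts every death, and a time-to-failure analysis. Failure includes any death during treatment. Section 8.3 does not name event-free survival, but much of its content is covered. This stands, but neither analysis corrects the curve labelled PFS.

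**The wording may be inherited.** Section 6.2.1 presents its criteria as IWG-2006, and the limit on cause is explicit. That is a reason to keep this version available, not to report it as PFS without a label.

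**Two points are inference.** No PFS censoring rule is written; censoring follows from the event definition and the estimator. The sentence in 8.3 on patients who discontinue before a clinical response concerns response and should not be read as such a rule. Nor do the documents say that the investigator decides cause of death for PFS; section 6.2.2 gives the investigator or a designee attribution of adverse events only. What stands is that the attribution rule is missing.

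**PFS carries little weight.** It appears as a secondary endpoint only in 8.3, not in the lists in 1.2, 6.2.3 or 8.1, and it has no target or decision rule. This stands and limits the severity.

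**Conclusion.** The concern holds as a fault in definition and labelling. The planned PFS estimate is insensitive to non-MDS deaths before progression and lies above the probability of being alive and progression-free. It does not rise with such deaths; it fails to fall.

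The direction is certain once any such death occurs. The size depends on a share that the documents do not give. The factor 1/(1 − share) also assumes constant hazards, and a 10-30% share corresponds to a median overstated by 11% to 43% (1/0.9 and 1/0.7). The estimate further depends on attribution of deaths for which no rule is stated.

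The consequence is confined to one descriptive secondary outcome in a single-arm trial of 40 patients. The primary response rate, the sample size and the futility and toxicity rules do not use PFS. A reader should not conclude that the trial's main result is at risk.

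**What to change.** In 6.2.1 and 8.3, define PFS as progression or death from any cause. Keep the MDS-death version as a supplementary estimate under a cause-specific label. Report it as the cumulative incidence of progression or MDS death, with other deaths as competing events, and state who attributes cause of death and by what rule, including for fatal bleeding and infection.

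The change alters text and one analysis, with no effect on sample size or monitoring. It needs no death data beyond those the planned overall survival analysis already requires. The schedule in 5.2 shows no visit after the 28-day safety visit, so how later deaths are captured is an open question for overall survival as well; this change does not create it.

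The cost is that PFS becomes slightly less favourable, and comparison with reports that use the MDS-death definition has to rely on the supplementary estimate.
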